## ABSTRACT

In the United States, depot medroxyprogesterone acetate (DMPA) is frequently administered prior to hospital discharge with the belief that women who delay initiation of DMPA may face higher risk of unintended pregnancy and that administration postpartum has little to no negative effect on breastfeeding. Administering DMPA to breastfeeding women has not been widely questioned because the limited existing studies do not show any adverse impact of DMPA on breastfeeding. However, these studies used inappropriate control groups and did not control for prior lactation experience.(1-3) We recently conducted a randomized controlled trial (RCT) which found that significantly fewer women who underwent immediate postplacental levonorgestrel-releasing IUD (LNG-IUD) placement continued to breastfeed at 6 months compared to those who underwent insertion at 6-8 weeks postpartum.(4) Since systemic levels of progestins are much less with the LNG-IUD compared to DMPA, we became concerned about potential effects of administering DMPA immediately postpartum.

We therefore propose to enroll 184 women who plan to breastfeed and use DMPA postpartum in a RCT to investigate whether the timing of postpartum administration of DMPA (prior to hospital discharge vs. 4-6 weeks postpartum) affects the duration or exclusivity of breastfeeding among women who plan to breastfeed their infants. Secondary outcomes will include rates of use of highly effective contraception (defined as DMPA, IUD, implant, sterilization, or lactational amenorrhea) and postpartum depression. Outcomes will be assessed by phone at 2, 4, 6, 8, 12, 16, 20, 24, and 28 weeks postpartum.

## 1. SPECIFIC AIMS AND HYPOTHESES

### SPECIFIC AIMS:

To compare the effect of administering postpartum intramuscular (IM) depot medroxyprogesterone acetate (DMPA) prior to hospital discharge compared to 4-6 weeks after delivery on: 1) exclusivity and duration of breastfeeding; 2) use of highly effective contraception; and 3) postpartum depression

### HYPOTHESES:

1. Women who receive DMPA 4-6 weeks after delivery will be more likely than women who receive DMPA prior to hospital discharge to exclusively breastfeed for 6 months.
2. Women who receive DMPA 4-6 weeks after delivery will be as likely as women who receive DMPA prior to hospital discharge to use highly effective contraception (i.e. DMPA, intrauterine device (IUD), implant, sterilization, or lactational amenorrhea) at 6 months after delivery.
3. Women who receive DMPA 4-6 weeks after delivery will be no more likely than women who receive DMPA prior to hospital discharge to develop postpartum depression as measured by the Edinburgh Postnatal Depression Scale.(5)

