### **3. RATIONALE**

DMPA is frequently given prior to hospital discharge in the US due to concerns that women will not follow-up for postpartum contraception. Given the severe limitations of currently published literature on breastfeeding following DMPA administration, and the recent study suggesting that immediate postplacental LNG-IUD insertion could negatively impact breastfeeding continuation, a properly performed randomized study to evaluate the use of immediate or delayed postpartum DMPA administration is needed. This study will be valuable in helping clinicians provide accurate advice to patients about potential effects of early DMPA administration on breastfeeding continuation, contraceptive use, and postpartum depression.

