#### *OUTCOME ASSESSMENTS*

- A questionnaire about breastfeeding (including psychosocial factors related to breastfeeding and introduction of alternatives to breastmilk) and contraceptive use will be administered at each contact. Timing of lactogenesis II will be assessed at Week 2 unless it occurred prior to discharge. Timing of postpartum sexual activity initiation will also be assessed. At any point when the subject reports cessation of breastfeeding, a questionnaire will be administered to assess reasons for discontinuation.

- The Edinburgh Postnatal Depression Scale (EPDS) will be administered at each contact as a screening tool for postpartum depression.(5) If a subject scores  $\geq 12$  on the EDPS, she will be referred to the Magee Behavioral Health clinic or to a behavioral health clinic of her choice and her primary obstetrician or midwife will be notified.
- Subjects will be asked if they had any visits with their primary obstetrician, midwife, or any other provider since the last contact. Records will be requested from all reported visits.
- The next telephone contact will be scheduled (when applicable).

**5.8 Data analysis:** Analysis will be performed using Stata 10 (StataCorp LP, College Station, TX).

- 1) The primary analyses will use intention-to-treat data. The intention-to-treat group will be defined as all randomized subjects. Infants who are fed pumped breastmilk will be considered as breastfeeding. Exclusive breastfeeding will be defined as breastfeeding without introduction of alternatives to breastmilk. A secondary analysis looking only at women who received at least one injection of DMPA will also be performed.
- 2) Survival analysis will be used for all time series data, including time to discontinuation of breastfeeding and time to introduction of alternatives to breastmilk. Data will be censored at the last date of contact. Breastfeeding will be the outcome variable. The log-rank test will be used for unadjusted comparison of the groups and presented graphically using a Kaplan-Meier curve. Cox proportional hazards model will be used to control for age, race, education, marital status, and prior breastfeeding experience while examining the association between timing of DMPA administration and discontinuation of breastfeeding.

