- 3) Normally distributed continuous variables will be compared using Student's t-tests. The Mann-Whitney rank-sum test will be used to compare other continuous variables. Proportions will be compared using chi-square tests or Fisher's exact tests as appropriate.

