### **5.9 Number of subjects and statistical power**

We previously found in a randomized study comparing postplacental and delayed LNG-IUD insertions that only 9% of subjects receiving a postplacental LNG-IUD were breastfeeding at 6 months compared to 41% of subjects receiving a delayed LNG-IUD.(4) We expect breastfeeding continuation rates will be higher in this study since we will be recruiting women who intend to breastfeed. A sample size of 70 per group achieves 80% power ( $\beta=0.20$ ) to detect a difference of 25% between the null hypothesis that the proportion of breastfeeding continuation at 6 months is 0.60 for both groups and the alternative hypothesis that the proportion in group 1 is 0.35 with a significance level of 0.05. With an estimated 10% discontinuation rate prior to randomization and 15% loss-to-follow-up, we plan to enroll 184 subjects

total. Sample size calculations were performed with the two-sided Fisher's Exact test using PASS 2005 (NCSS, Kaysville, UT).

Group 1 (on discharge)	Group 2 (4-6 weeks)	Sample size per group	Total sample size	Including 10% discontinuation/15% LTFU
0.15	0.4	56	112	147
0.25	0.5	64	128	168
0.35	0.6	70	140	184
0.45	0.7	69	138	182

**5.10 Project management:** The study will be coordinated by the Center for Family Planning Research, located in Magee-Womens Hospital at the University of Pittsburgh, which has performed a broad array of family planning research since 1994. The principal investigator and the research coordinator will be responsible for daily monitoring of subject safety. Enrollment, outcomes, and adverse events will be reviewed during biweekly meetings of the investigators and staff. The office has locked storage areas for maintaining subject files. All computers used for database management have firewalls and antivirus software that are updated regularly.

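### Hypotheses 2 and 3 claim similarity and no excess, but the plan gives them only tests of difference, with no margin or confidence-interval rule, so a non-significant p-value can support neither.

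*Combined protocol and SAP*

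**What the plan says.** Section 1 gives three hypotheses. The first, on exclusive breastfeeding, is a superiority claim. The other two are not:

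- Hypothesis 2: women given DMPA at 4-6 weeks "will be as likely as women who receive DMPA prior to hospital discharge to use highly effective contraception" at 6 months.
- Hypothesis 3: these women "will be no more likely than women who receive DMPA prior to hospital discharge to develop postpartum depression", as measured by the Edinburgh Postnatal Depression Scale (EPDS).

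The Abstract lists both outcomes as secondary. Section 5.7 says that the EPDS "will be administered at each contact as a screening tool for postpartum depression", which means nine times.

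The methods are in section 5.8. Item 3 says "Proportions will be compared using chi-square tests" or Fisher's exact test. For continuous measures it gives the t-test, and "The Mann-Whitney rank-sum test will be used to compare other continuous variables". Item 2 provides log-rank and Cox methods and adds "Breastfeeding will be the outcome variable". Section 5.9 sizes the trial on breastfeeding only, with a null hypothesis that "the proportion of breastfeeding continuation at 6 months is 0.60 for both groups".

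No section states a margin, a confidence-interval rule or a power figure for contraception or depression.

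**The concern.** Hypothesis 2 is worded as an equivalence claim and Hypothesis 3 as a non-inferiority claim. A test of no difference can reject equality, but failing to reject it does not show that a difference is small. So the result to be expected when the hypotheses are true is one the plan cannot turn into support for them. Hypothesis 3 has one partial exception: a significantly lower depression rate in the delayed arm would support it. Under the wording of Hypothesis 2, no significant two-sided result does.

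This matters for what the trial is meant to deliver. Section 3 says it should help clinicians advise on "potential effects of early DMPA administration on breastfeeding continuation, contraceptive use, and postpartum depression". Section 5.11 expects women to weigh the contraceptive benefit of the early injection against a possible effect on breastfeeding. Such advice depends on how large a loss of contraceptive use, or rise in depression, with delay has been ruled out. A p-value above 0.05 does not say.

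**Working it through.** **Inputs from the documents.** 70 per arm and two-sided alpha 0.05 (section 5.9). 140 women expected at weeks 16-28 and 165, or about 82 per arm, through week 12 (Budget justification). Postpartum depression in 10%-15% of mothers (section 2).

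**Assumptions.** The documents give no rate of contraceptive use; 50%-80% is used for precision and margins, and 60%-80% as the starting level for a 15-point fall. An EPDS-defined depression rate of 20%-30% is shown as an alternative. The margins of 10 and 15 points are illustrative only.

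**The plan's own figure.** Exact enumeration of the two-sided Fisher test for 0.35 versus 0.60 gives power 0.809 at 70 per group and 0.799 at 69, so the stated 70 is confirmed. Enrolment: 140/(0.90 × 0.85) = 183.0, against 184 stated.

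**1. How often the planned test gives p>0.05 when the hypothesis is false.** Two independent binomials, enumerated exactly:

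| True rates (discharge vs 4-6 weeks) | n per arm | Fisher | Chi-square, uncorrected |
|---|---|---|---|
| Depression 10% vs 20% | 70 | 0.695 | 0.618 |
| Depression 12.5% vs 25% | 70 | 0.598 | 0.519 |
| Depression 15% vs 30% | 70 | 0.506 | 0.423 |
| Depression 10% vs 20% | 82 | 0.643 | 0.566 |
| Depression 15% vs 30% | 82 | 0.432 | 0.356 |
| Contraception 80% vs 65% | 70 | 0.561 | 0.480 |
| Contraception 70% vs 55% | 70 | 0.619 | 0.553 |
| Contraception 60% vs 45% | 70 | 0.632 | 0.566 |

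The depression rows are a stress case. The one directional finding cited in section 2 is more depression after an early injectable progestin.

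**2. How often the planned test supports Hypothesis 3 when it is true.** Probability of p≤0.05 with the lower rate in the delayed arm, 70 per arm:

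- Delay halves depression (20% to 10%, up to 30% to 15%): 0.305 to 0.494 by Fisher, 0.382 to 0.577 by chi-square.
- Equal rates of 10%-15%: 0.013 to 0.015 by Fisher, 0.025 to 0.026 by chi-square.

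**3. What a confidence interval would show.** Half-width of the 95% interval for a risk difference with equal rates p is 1.96 × √(2p(1−p)/n). For p = 0.10 and n = 70 this is 1.96 × √(0.18/70) = 0.099.

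| Outcome | Rate | n per arm | Half-width, points |
|---|---|---|---|
| Depression | 10%-15% | 70 | 9.9 to 11.8 |
| Depression | 10%-15% | 82 | 9.2 to 10.9 |
| Depression (assumed rate) | 20%-30% | 70 | 13.3 to 15.2 |
| Contraception (assumed rate) | 80%-50% | 70 | 13.3 to 16.6 |

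**4. Whether a margin could be met.** Exact enumeration with Wald 95% limits, equal true rates, 70 per arm:

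- Depression, upper limit below 10 points: 0.532 at 10%, 0.397 at 15%, and 0.318 to 0.258 at 20%-30%.
- Contraception, both limits inside ±15 points: 0.000 at 50% and 60%, 0.035 at 70%, 0.223 at 80%.
- Contraception, lower limit only above −15 points: 0.412 at 50%, 0.611 at 80%.

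**The case against.** The strongest reply is that the error is only potential. Item 3 of section 5.8 is a general list of tests that names neither hypothesis. The aims in section 1 are neutral comparisons, so the hypotheses can be read as the investigators' expectations. Nothing says that p>0.05 will be taken as equality, and nothing prevents intervals from being reported. All of that is true. It does not supply a rule, and a reader who follows the plan as written obtains only a p-value.

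Item 2 extends survival analysis to time series data in general, which could be stretched to time to a positive EPDS. The sentence naming breastfeeding as the outcome points the other way, and the log-rank test is in any case another test of difference without a margin.

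The magnitudes for contraception depend on assumptions, and here the objection has force. The worry about delay is mainly one-directional, so Hypothesis 2 may fairly be read as non-inferiority, and a 15-point margin would then be met in 41%-61% of trials instead of 0%-22%. At 90% use the figures are 84% one-sided and 68% two-sided, and a 15-point fall from 90% would give p>0.05 in only 34%-42%. These points soften the illustrations. They do not supply the missing rule.

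Finally, both outcomes are secondary, which limits the weight of the point.

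**Conclusion.** The concern holds, with high confidence on the mismatch itself: two hypotheses claim similarity or no excess, and every method offered tests for a difference. At 70 per arm a non-significant result would be the usual one if the arms were equal, and also common (roughly 40%-70% of trials) if depression doubled from 10%-15% or contraceptive use fell by 15 points from an assumed 60%-80%. It therefore cannot separate the two situations. The depression figures rest on the 10%-15% rate cited in section 2. The contraception rates and all margins are assumptions. Two secondary conclusions are affected. The breastfeeding comparison and its sample size, which reproduces, are not. The plan should be changed on this point.

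**What to change.** In section 5.8, item 3, state that highly effective contraception at 6 months and postpartum depression will each be analysed as the risk difference, 4-6 weeks minus pre-discharge, with a two-sided 95% confidence interval (a mean difference with its interval if the EPDS is kept as a score). Reword Hypotheses 2 and 3 as estimation objectives, and state that p>0.05 will not be reported as no difference.

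Give the expected half-widths with their assumptions: about ±13 to ±17 points for contraceptive use at 70 per arm (assumed 50%-80%); about ±9 to ±12 points for depression at 10%-15%; and about ±13 to ±15 points at 70 per arm if the EPDS-defined rate is 20%-30% (assumed). Because the depression width depends on it, state in advance how the nine EPDS contacts form the outcome.

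A margin is optional. If the sponsor can justify one in advance, Hypothesis 3 needs only the upper limit below it. Hypothesis 2 read as equivalence needs both limits inside it; read as non-inferiority, it needs only the lower limit above the negative margin. The reading should be stated.

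The cost is wording in the protocol and SAP, with no new data or enrolment. Section 5.11 shows that recruitment was already under way, so this would go through as a formal modification. The two secondary conclusions become more cautious, and at this size a margin-based claim would often fail even if the arms were truly equal.

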## 2. PREVIOUS RESEARCH

Postpartum contraception is important because unintended pregnancy rates range from 10%-20% in the first year postpartum.(6, 7) Lactational amenorrhea (LAM) can be effective contraception for up to 6 months.(8) However, many US women stop breastfeeding soon after delivery. By two weeks postpartum, an estimated 59% of US women started supplementation (2) and 37% of women stopped breastfeeding.(9) If sexually active and not using contraception, such women are at risk for unintended pregnancy.

Postpartum visits in the US generally occur 4-6 weeks after delivery.(10) Although 85% of women return for postpartum visits,(11) approximately half of women initiate sexual activity before six weeks postpartum and 82% are sexually active by 12 weeks postpartum.(12) Since ovulation can occur by 4 weeks postpartum in non-breastfeeding women,(13) experts recommend that women who are not exclusively breastfeeding should initiate contraception by 3 weeks postpartum.(14) Some also recommend that the postpartum visit should occur by 2-4 weeks postpartum in order to address contraception, breastfeeding, and postpartum depression,(14, 15) since postpartum depression affects 10%-15% of mothers (16) and can be associated with poor maternal-infant interactions and attachment.(17) Studies of the association of depression and breastfeeding discontinuation are conflicting.(18-20) One study of norethisterone enanthate given within 48 hours of delivery found an increased risk of postpartum depression,(21) but no studies have examined the effect of timing of DMPA administration on postpartum depression, contraceptive use, or breastfeeding.

Breastfeeding has many benefits, including immunologic protection and nutrition for the infant, more rapid uterine involution, decreased postpartum bleeding, and improved infant-bonding.(22) Exclusive breastfeeding for at least six months is recommended by the American College of Obstetricians and Gynecologists and the World Health Organization.(22, 23) However, only 41% of children in the National Immunization Survey were breastfed for 6 months.(24)

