- 1.) Group 1: An investigator will order DMPA to be administered prior to hospital discharge. The subject's subsequent DMPA injection will be due 11-13 weeks after the injection. The subject will follow up with her primary obstetrician or midwife for further DMPA administrations.
- 2.) Group 2: The subject will be asked to follow up with her primary obstetrician or midwife at 4-6 weeks after delivery for DMPA administration or to start a more effective form of contraception such as an IUD or implant, or to be scheduled for sterilization. She will be instructed to use condoms until her follow-up visit if she is not abstinent. She will also be instructed on emergency contraception use.

A questionnaire about breastfeeding intentions and whether lactogenesis II has occurred (i.e. the mother's "milk has come in") will be administered prior to discharge. Information about the delivery and postpartum course will be collected, including type of delivery, birth weight, gestational age, Apgar scores, and subject's height and weight at time of delivery. The subject's primary obstetrician or midwife will be notified of plans for administering the woman's next dose of DMPA. Routine postpartum care (including referrals for lactation consultation or behavioral health services) will be provided by the subject's primary obstetrician or midwife. Any subject who decides to use an alternate form of contraception after randomization will be followed per protocol. The 2-week follow-up phone contact will be scheduled prior to discharge.

**5.7 Follow-up contacts:** Subjects will be contacted by phone at the following time points:

1) Week 2: day 12-19 (goal day 14)	6) Week 16: day 108-118 (goal day 112)
2) Week 4: day 26-33 (goal day 28)	7) Week 20: day 136-146 (goal day 140)
3) Week 6: day 40-47 (goal day 42)	8) Week 24: day 164-174 (goal day 168)
4) Week 8: day 54-61 (goal day 56)	9) Week 28: day 192-202 (goal day 196)
5) Week 12: day 80-90 (goal day 84)	

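### Hypothesis 3 claims that delayed DMPA brings no more depression but sets no margin, and at about 70 per arm a non-significant test cannot support reassurance about timing in either direction

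*Combined protocol and SAP*

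**What the plan says.** Hypothesis 3 (section 1) states that women in the 4-6 week group will be "no more likely than women who receive DMPA prior to hospital discharge to develop postpartum depression", as measured by the Edinburgh Postnatal Depression Scale (EPDS). It gives no margin. The third specific aim is neutral: it compares the two timings without naming a direction.

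Section 2 cites one piece of evidence on a progestin injection and depression: "One study of norethisterone enanthate given within 48 hours of delivery found an increased risk of postpartum depression". The same sentence adds that "no studies have examined the effect of timing of DMPA administration on postpartum depression, contraceptive use, or breastfeeding". It also gives a background rate: "postpartum depression affects 10%-15% of mothers".

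Under the outcome assessments in section 5.7, the EPDS "will be administered at each contact as a screening tool for postpartum depression". A score of 12 or more triggers referral, but the text does not say that this cut-off defines the outcome, and it names no time point for the depression comparison. Section 5.8 compares proportions by chi-square or Fisher's exact test, with no one-sided or non-inferiority test. Section 5.9 sizes the trial for breastfeeding at 6 months only.

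**The concern.** A statement that one arm is no worse than the other needs a margin, or at least an interval, before data can support it. The plan offers neither for depression. What remains is a significance test in a trial sized for a 25-point difference in another outcome. In practice a p-value above 0.05 is likely to be reported as agreement with Hypothesis 3.

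The wording adds to the difficulty. It asks only whether delay carries more depression, while the evidence that the protocol itself cites points to early dosing. A real excess in the immediate arm could be missed by the test, and the result could still be written up as consistent with the hypothesis. Clinicians could then read it as showing that timing does not matter for mood. The protocol intends its results to inform advice to patients on exactly this (section 3).

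**Working it through.** **1. The plan's own figure.** Inputs from section 5.9: 0.35 vs 0.60, two-sided 0.05, 80% power, Fisher's exact test. Exact enumeration at 70 per arm gives power of 80.9%, so 70 per arm is reproduced. Inflation is 140 / (0.90 × 0.85) = 183.0, against 184 stated. No corresponding figure is given for depression.

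**2. Power for depression at 70 per arm.** The delayed-arm rate is taken from the 10%-15% background in section 2. The doubling in the immediate arm is an assumption, because the documents give no effect size.

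Formula for chi-square: power = Φ{[d√n − 1.96√(2p̄(1−p̄))] / √(p₁(1−p₁) + p₂(1−p₂))}, where d is the difference and p̄ the mean rate.

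For 20% vs 10%: d√n = 0.10 × 8.367 = 0.837; 1.96 × √(2 × 0.15 × 0.85) = 0.990; denominator √(0.16 + 0.09) = 0.50. Power = Φ(−0.306) = 38%.

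| Immediate vs delayed (assumed) | Chi-square | Fisher's exact (enumerated) | n per arm for 80% power (chi-square) |
|---|---|---|---|
| 20% vs 10% | 38% | 30.5% | 199 |
| 25% vs 12.5% | 47% | 40% | 152 |
| 30% vs 15% | 57% | 49% | 121 |

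**3. What a non-significant result leaves open.** Suppose 14 of 70 and 7 of 70 are observed (20% vs 10%). The standard error is √[(0.20 × 0.80 + 0.10 × 0.90)/70] = √(0.25/70) = 0.0598. The 95% interval for immediate minus delayed is 0.10 ± 1.96 × 0.0598, or −1.7 to +21.7 points. The p-value is about 0.10 by chi-square and 0.15 by Fisher. An observed doubling would therefore be non-significant.

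Suppose instead that both arms show 10%. The standard error is √(2 × 0.09/70) = 0.0507 and the interval is ±9.9 points. Identical observed rates would still be compatible with an excess of almost 10 points in either arm.

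**4. Which contacts precede the delayed injection.** Section 5.7 places the week 2 contact at days 12-19, and the next at "2) Week 4: day 26-33 (goal day 28"). Group 2's injection is due at 4-6 weeks, so from day 4 × 7 = 28. Week 2 falls before it. The week 4 window runs to day 33 and can overlap it, so a week 4 score may come before or after the injection.

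**The case against.** The strongest reply is that the plan already allows the right comparison. Aim 3 names no direction, the tests respond to a difference either way, and EPDS scores are collected from week 2. A reader might infer from the wording of Hypothesis 3 that the trial cannot say whether DMPA before discharge raises depression. The documents do not support that: the same comparison estimates an excess in either arm. A reader might also count it as a flaw that harm in the immediate arm would almost never contradict Hypothesis 3. But the hypothesis would then be true, and failing to contradict a true statement is no error.

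The wording also has a coherent purpose. All three hypotheses take the delayed arm as subject, and together they can be read as asking whether delay helps breastfeeding without a cost in contraception or mood. The documents do not state this intent, but the question is legitimate.

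The evidence for early harm is thin: one study, of another progestin, whose title in the reference list describes a placebo control and not a comparison of timings. The Abstract's statement that "we became concerned about potential effects of administering DMPA immediately postpartum" follows from a breastfeeding result. Nor do the documents present depression as the trial's maternal-safety outcome; the Abstract lists it as secondary.

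Finally, a reader might infer that contacts after week 6 would wash out an early excess. No average over contacts is planned, and an outcome counted as ever screening positive would keep early cases. Section 5.11 also expects that many women may stop DMPA or not start it at 4-6 weeks, so later exposure in the two arms cannot be taken as equal.

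All of this stands. It leaves untouched the absence of a margin and the low power, which together decide what a non-significant result can mean. Rewording does not raise the power; it changes only the conclusion that may be drawn.

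**Conclusion.** The point holds as one about inference. Hypothesis 3 claims no excess in one direction, without a margin, and the planned tests have about 30.5% to 57% power for a doubling, depending on the test and on a delayed-arm rate between 10% and 15%. At the lower rate the range is 30.5% to 38%, so such an excess would be missed in about two trials of three. A p-value above 0.05 would therefore not support a claim that timing is immaterial to depression, nor show that either timing is free of excess risk.

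The figures assume 70 analysed per arm, a single yes/no depression outcome (which the plan has not yet defined) and an assumed doubling. The consequence is limited: depression is a secondary outcome, the data will be collected, and only the statement of the hypothesis and the rule for interpreting it need to change.

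**What to change.** - Restate Hypothesis 3 as a two-sided contrast, immediate minus delayed, in line with Aim 3. This still covers the question of whether delay carries a cost.
- Report the difference in proportions with its 95% confidence interval. Base reassurance about immediate DMPA on the upper limit and reassurance about delayed DMPA on the lower limit, not on p > 0.05. State the limited power for this outcome.
- Fix the EPDS cut-off and time point, or period, that define the outcome over full follow-up.
- Alongside that comparison, prespecify an early EPDS comparison at week 2. Treat week 4 as supportive and check its scores against actual injection dates. Keep later contacts in the report.

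This costs protocol and SAP wording only; no new data or participants are needed. The downside is that the interval will be wide and the conclusion on depression more modest. The early comparison also rests on one clean contact.
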